3.1.1. Description of target group

The aim of both studies is to detect early risk for problematic internet use and prevent the development of addictive usage patterns across the whole well-being spectrum, rather than to treat an already developed pathological use. The whole adolescent population is therefore included rather than specific subgroups. The study population will consist of young adolescents of all genders between 12 and 16 years, recruited from schools with different socioeconomic backgrounds and from rural and urban areas. We strive to include young people from low/middle income families who might be especially vulnerable for PUI. The BootStRaP study is designed to evaluate and moderate online behaviour among young people using mobile devices. Therefore, it is a necessary condition, that young people involved have routine and exclusive access to a mobile device to be able to take part in the study.

The eligibility criteria are:

- Age between 12 and 16 years
- Routine access to a mobile device
- Student at a school involved in the study

The exclusion criteria are:

- No exclusive access to a mobile phone
- Phone operating systems older than 15.6 for iOS or 10 for Android

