4.6. Intervention

In both the pilot and RCT study interventions (emotional regulation, inhibitory control and control) as described in section 3.2 will be delivered and completed through the app (see table 2 for a breakdown intervention tasks). On average, participants are asked to complete assigned tasks of the intervention (or for the control group, read presented information) every 2 days over a period of 4 consecutive weeks. The tasks will be delivered through the BootstrApp intervention app with participants being notified of a task to complete via automated push notification.

Within the two intervention arms (targeting emotional regulation or inhibitory control), participants are categorised according to their risk for PUI, using the baseline S-CUIS score with scores of ≥ 9 indicating high risk of PUI. Participants at high risk for PUI are given access to additional intervention elements that either address emotion regulation or inhibitory control in the context of problematic Internet use.

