6.1.1. Assessment tools

Demographic information.

Questions on demographic information at T0 include age, year group at school, sex, gender and any current mental health diagnosis such as ADHD, OCD, Depression etc. The study unique code (see section 4.3) encodes participant's school and country of residence.

Core Determinants and Outcomes

PUI and clinical variables

- The **Compulsive Internet Use Scale** (CIUS) (Meerkerk et al., 2009) will be used in its 5-item short version (S-CIUS) (Besser et al., 2017) and is the primary outcome measure in this study and assesses severity of compulsive internet use. A cut-off of 9 will be used to determine high risk of PUI as identified during the assessment phase.
- The **Problematic Internet Use Questionnaire** (PIUQ) (Demetrovics et al., 2008) will be used in a shorter version (PIUQ-9) (Laconi et al., 2019). The PIUQ-9 assesses three aspects of PUI: obsession, neglect and control disorder.
- The **Internet Severity and Activities Addiction Questionnaire** (ISAAQ-10 (Ioannidis et al., 2023)(Part B) assesses which kinds of activities are done on the internet. Additionally, the ISAAQ-ED (Ioannidis & Chamberlain, 2020) captures internet activities related to eating disorders. Psychometric properties of scales have been evaluated and confirmed (Ioannidis et al., 2023)
- A short version of the **Assessment of Criteria for Specific Internet-use Disorders** (ACSID-11; (Müller et al., 2022)), the ACSID-5 will be used to measure the extent of symptom severity for the most prominent forms of problematic internet use behaviours (i.e., gaming, gambling, social networking, buying-shopping, pornography use) (Müller et al., 2022).
- The 21 Item version (DASS-21) (Lovibond & Lovibond, 1995; Szabó, 2010) of the **Depression Anxiety Stress Scale** (Lovibond & Lovibond, 1995) used to assess symptoms of depression, anxiety, and levels of stress.
- The **Paediatric Self-Stigmatization Scale** (PaedS) (Kaushik et al., 2017) measures self-stigma in children.
- In addition, participants will also be asked about their **Mood** using a mood barometer.
- The Short **Obsessive Compulsive Disorder Screener** (SOCS) (Piqueras et al., 2015; Uher et al., 2007) will be used as self-report measure for obsessive compulsive disorder symptoms.
- The **Strengths and Difficulties Questionnaire** (SDQ) (Goodman, 2001) will be used to assess emotional and behavioural difficulties.

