To account for missing data, we will apply multiple imputation techniques, maintaining data integrity and robustness in the economic analysis. Both intent-to-treat and complete case analyses will be conducted, complemented by probabilistic sensitivity analysis to account for variability in economic inputs and costs across different study sites.

A key component of the health economic analysis will be the measurement of Health-Related Quality of Life (HRQoL). We will use two validated scales to provide a balanced assessment of mental health impacts:

- The Paediatric Quality of Life Enjoyment and Satisfaction Questionnaire (PQ-LES-Q) (Endicott et al., 2006) will serve as the primary utility scale. This instrument is particularly suitable for adolescents, as it captures relevant domains and is sensitive to the factors most likely influenced by PUI interventions.
- The EQ-5D-Y (Wille et al., 2010) will be included as a secondary outcome measure. This short (2-minute) and user-friendly tool offers a visual analogue version, which enhances its applicability in diverse settings.

Using both HRQoL measures will enable us to address content validity concerns with existing instruments, especially given that many available quality of life scales favour physical health outcomes over mental health. By leveraging BootStRaP's large, cross-country sample size, we aim to enhance the validity and generalizability of our findings across European contexts.

The economic outcomes will be expressed in terms of societal costs, converted to Quality-Adjusted Life Years (QALYs). We will present the costs of interventions through two primary metrics: incremental costs per QALY gained and incremental costs per adolescent with PUI in full remission. These metrics will provide clear insights into the value for money of the BootStrApp interventions, supporting evidence-based decision-making for policy and practice.

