8.1.1. Risk-Benefit Assessment

The pilot study and RCT will build on the findings of the assessment study, offering unprecedented insights into the psychological mechanisms underlying PUI risk, the early detection of at-risk adolescents, and effective preventative interventions. The BootStRaP project aims to develop evidence-based policy recommendations that could significantly contribute to the prevention of problematic internet use across Europe.

The study's robust recruitment strategy, which includes adolescents from nine European countries with diverse genders, socioeconomic backgrounds, and geographical areas (rural and urban), enhances the generalisability of the results.

The risk to participants is expected to be minimal, as the health lifestyle and well-being interventions are designed to prevent PUI, a behavioural issue not a clinical condition, rather than to treat a medical disorder. The study purpose is clearly explained to participants beforehand, including information on the questions asked and potential interventions offered.

Participation is entirely voluntary, and participants can withdraw at any time without providing a reason. If emotional distress arises, the study app includes a dedicated help submenu, guiding participants and, where appropriate, their parents to local mental health support services for children and adolescents.

The study places a strong emphasis on data protection, confidentiality, and anonymity, as detailed in Data Management (Section 6.2) and Data Protection and Participant Confidentiality (Section 11).

The pilot study and RCT are expected to benefit participants by:

- Reducing their risk of PUI.
- Enhancing emotional regulation and inhibitory control strategies, depending on the allocated intervention.

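### One of the two primary economic metrics counts only full remission, so it gives no credit for the prevented onsets that this whole-population prevention trial aims for

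*Protocol*

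**What the plan says.** - **Economic metrics.** Protocol section 6.3.3 names "two primary metrics: incremental costs per QALY gained and incremental costs per adolescent with PUI in full remission". Cost-effectiveness and cost-utility are the stated secondary objective of the RCT (Study Summary and section 2.1).
- **Aim and population.** Section 3.1.1 says the studies are to detect early risk and "prevent the development of addictive usage patterns across the whole well-being spectrum, rather than to treat an already developed pathological use". It adds: "The whole adolescent population is therefore included rather than specific subgroups". Section 8.1.1 calls PUI "a behavioural issue not a clinical condition, rather than to treat a medical disorder".
- **Who is treated.** Sections 3.2 and 4.6 give the interventions to low-risk and high-risk participants alike. The high-risk group gets additional modules and the low-risk group gets general guidance.
- **Threshold.** Section 4.6 classifies participants "using the baseline S-CUIS score with scores of ≥ 9 indicating high risk of PUI". Section 6.1.1 repeats the cut-off of 9. Both attach it to high risk, not to PUI as a condition.
- **Share at risk.** Section 3.4.2 assumes 30% high risk and 70% completion.

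**The concern.** A cost-effectiveness ratio should use an effect unit that matches what the intervention is meant to achieve. Here the unit is an adolescent who already has PUI and then remits. An adolescent who starts below the threshold and would have crossed it without the intervention, but did not, is a success by the aim in section 3.1.1. That adolescent still adds nothing to the effect side of this metric.

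This follows from the choice of unit. It is not a detail that a later analysis plan would fill in: such a plan could define remission, but it could not credit prevented onsets without replacing the unit. Section 6.3.3 intends these metrics to inform policy and practice decisions. A reader of the remission ratio alone would see the treatment effect of a prevention programme and none of its prevention effect.

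**Working it through.** **1. The protocol's own figures.** A two-sided test at α = 0.05 with power 0.80 and d = 0.3 needs 175.4 per group, rounded up to 176. Then 176 / 0.3 / 0.7 = 838 per group and 3 × 838 = 2514, as section 3.4.2 states. On the same assumptions, 838 × 0.3 ≈ 251 participants per arm start at high risk and 838 × 0.7 ≈ 587 do not. The remission metric can register benefit only in the first set.

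**2. Model for the illustration.** From the protocol: 30% above the cut-off, and d = 0.3 as the effect in high-risk participants. Assumed, because the protocol gives no values: scores at baseline and follow-up are bivariate normal with correlation r between 0.6 and 0.8; remission means falling below the cut-off; the shift s in low-risk participants is 0.3, 0.15, 0.1 or 0 SD.

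The standardised cut-off is c = 0.524 (the 70th percentile). Φ₂(·,·;r) is the bivariate normal distribution function. Per 1,000 participants:

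- Extra remissions = 1000 × [Φ₂(−c, −c; r) − Φ₂(−c, −c−0.3; r)]
- Prevented onsets = 1000 × {[Φ(−c) − Φ₂(−c, −c; r)] − [Φ(−c−s) − Φ₂(−c, −c−s; r)]}
- Share missed = prevented onsets / (extra remissions + prevented onsets)

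**3. Results per 1,000.** Each cell in the last four columns gives prevented onsets and the share missed.

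| r | Extra remissions | s = 0.3 | s = 0.15 | s = 0.1 | s = 0 |
|---|---|---|---|---|---|
| 0.6 | 41.8 | 53.4 (56%) | 29.1 (41%) | 19.9 (32%) | 0 (0%) |
| 0.7 | 44.6 | 50.5 (53%) | 27.9 (38%) | 19.2 (30%) | 0 (0%) |
| 0.8 | 48.3 | 46.9 (49%) | 26.5 (35%) | 18.4 (28%) | 0 (0%) |

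Example for r = 0.6 and s = 0.15: 29.1 / (41.8 + 29.1) = 41%.

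Check for s = 0.3: prevalence above the cut-off falls from 30.0% to Φ(−0.824) = 20.5%, which is about 95 fewer cases per 1,000. This agrees with 41.8 + 53.4, 44.6 + 50.5 and 48.3 + 46.9.

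**4. Reading.** The share missed changes little with r and strongly with s. The size of the gap therefore depends mainly on whether low-risk participants benefit.

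**The case against.** Much of the case on the other side stands.

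- **Cost per QALY covers everyone.** The companion metric is not confined to adolescents with PUI, so the economic evaluation as a whole does not ignore prevention. This stands and limits the point to one metric.
- **Remission is not foreign to the design.** The Study Summary also aims to reduce problematic behaviour patterns, section 3.4.2 sizes the trial on high-risk completers, and section 6.3.3 plans a benchmark against OCD and gambling disorder. This is a good reason to keep remission, but not to make it the only clinical effect unit among the primary metrics.
- **The effect size belongs to high-risk participants.** Section 3.4.2 sets d = 0.3 for them, and low-risk participants get lighter content. This stands. The equal-shift column is an upper case, and the range down to 0% has to be shown.

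A reader might also infer three stronger points that the protocol does not support.

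- **That remission is met by chance in about a third of high-risk participants, which invalidates the metric.** That figure needs an assumed correlation near 0.75 and an assumed rule of S-CIUS below 9. Under the same rule it runs from 21% to 48% for r from 0.9 down to 0.5, and a stricter rule gives less. The metric is also incremental: regression to the mean is equal in expectation across randomised arms and cancels. It adds noise, not bias.
- **That S-CIUS 9 is the only cut-off, so remission must mean crossing it.** Appendices A and B hold CIUS bands for in-app feedback, and section 6.3.3 names no instrument for remission. The remission rule itself may sit in an analysis plan that is not shown, so its absence is no finding.
- **That cost per case is doubled.** This compares two different units, needs the equal-shift case, and assumes that the costs of all participants enter the remission ratio, which the protocol does not state.

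**Conclusion.** The point holds as a mismatch between metric and aim. As written in section 6.3.3, the second primary economic metric gives no credit for prevented onsets in a trial that enrols and treats the whole adolescent population in order to prevent PUI. Under the assumptions in the working, it leaves out 28–56% of the reduction in above-threshold cases when the low-risk shift is between 0.1 and 0.3 SD. It leaves out nothing if low-risk participants do not respond. The correlation, the normal model, the remission rule and the low-risk shift are all assumptions, so these figures illustrate the gap and do not estimate it. The matter concerns a secondary objective and one metric of two. It is a worthwhile and inexpensive improvement, not a flaw that threatens the trial's main conclusions.

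**What to change.** In section 6.3.3, replace the second primary metric with the incremental cost per case at or above the high-risk threshold averted. The effect is the between-arm difference in the proportion with S-CIUS of 9 or more at T2 among all randomised participants, adjusted for baseline S-CIUS. Remissions and prevented onsets then both count. Label these cases high risk of PUI, as the protocol does ("scores of ≥ 9 indicating high risk of PUI"), and do not call them PUI cases.

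Keep full remission among participants at high risk at baseline as a supportive metric, so that the comparison with OCD and gambling disorder remains possible.

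The cost is a change of wording in section 6.3.3 and one small additional analysis. S-CIUS is already scheduled at T0 and T2 (Table 1). The downside is that the headline ratio becomes less directly comparable with treatment trials; the supportive metric covers that use.

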8.1. Risk Assessment

QA and QC considerations for the study should be based on the formal risk assessment performed, that acknowledges the risks associated with the conduct of the study and proposals of how to mitigate them through appropriate QA and QC processes. Risks are defined in terms of their impact on the rights and safety of participants; project concept including trial design, reliability of results and institutional risk; project management; and other considerations.

The Project Office (PO) will overview the overall risk management of the project. In case a partner identifies a risk for the project he/she must fill the risk assessment Form. The risk assessment form can be found in the trial master file folder of the BootStRaP Teams channel. All risk assessment forms must be logged as a file note and on the file note log and sent to the Project Office for review.

Risk will be constantly evaluated by the PO and evaluated depending on the severity of consequences and chance of happening through an overall Risk Matrix. All reported risks will be entered into the risk management register and mitigation for these risks identified. Progress and barriers to progress will be

monitored and solutions sought from the SC, and the Advisory Boards as required to enable any issues to be resolved in a timely fashion.

8.1.1. Risk-Benefit Assessment

The pilot study and RCT will build on the findings of the assessment study, offering unprecedented insights into the psychological mechanisms underlying PUI risk, the early detection of at-risk adolescents, and effective preventative interventions. The BootStRaP project aims to develop evidence-based policy recommendations that could significantly contribute to the prevention of problematic internet use across Europe.

The study's robust recruitment strategy, which includes adolescents from nine European countries with diverse genders, socioeconomic backgrounds, and geographical areas (rural and urban), enhances the generalisability of the results.

The risk to participants is expected to be minimal, as the health lifestyle and well-being interventions are designed to prevent PUI, a behavioural issue not a clinical condition, rather than to treat a medical disorder. The study purpose is clearly explained to participants beforehand, including information on the questions asked and potential interventions offered.

Participation is entirely voluntary, and participants can withdraw at any time without providing a reason. If emotional distress arises, the study app includes a dedicated help submenu, guiding participants and, where appropriate, their parents to local mental health support services for children and adolescents.

The study places a strong emphasis on data protection, confidentiality, and anonymity, as detailed in Data Management (Section 6.2) and Data Protection and Participant Confidentiality (Section 11).

The pilot study and RCT are expected to benefit participants by:

- Reducing their risk of PUI.
- Enhancing emotional regulation and inhibitory control strategies, depending on the allocated intervention.

Participating schools have become part of international research on PUI and can influence how the study is conducted (see section 9). They have access to a network of PUI experts and are featured on the project website if they choose. In addition, schools can receive anonymous feedback if they wish. Educational input (e.g. Informative presentations for students or parents) can be offered by the recruitment centres depending on the interest of schools. School ambassadors will be involved in designing feedback and educational inputs for schools. Materials for developing educational input are already available on the BootStRaP website [Net and Me - BOOTSTRAP \(internetandme.eu\)](http://Net and Me - BOOTSTRAP (internetandme.eu)). Any feedback or educational inputs are only provided after completion of the data collection, to avoid biasing the study results. Schools and educators will gain access to the intervention materials at the end of the project, enabling ongoing use within educational settings. The project's findings will also provide long-term benefits to future individuals at risk of PUI.

Participants will receive a certificate and a monetary voucher as a token of gratitude for their time and effort, promoting engagement and recognising their contribution to the research.

8.2. Monitoring

The UoH QMS will be adapted to provide study specific documents relating to data monitoring and integrity.

The data will be monitored on a weekly basis by the co-ordinator or a delegated individual, and data integrity monitored on a routine basis by an independent monitor. Part of the monitoring process will include identifying systematic data errors either at study sites, or due to systematic structural issues with the data collection process. Where required, a data recovery process will be recorded and specified, and training of all relevant individuals will be undertaken to ensure that ongoing errors are avoided. Serious data breaches will be reported within 48 hours to the sponsor and to the PI at the concerned study site. The breach will be followed up within 7 days to ensure that appropriate action is taken by the study team and by the relevant organisations involved.

Study adherence will be centrally monitored via the mobile app and automated reminders will be sent (based on ethical protocols). Monitoring of data collection is done via the “BootStRaP Analytics” Dashboard (an internal website accessible for recruitment centres). Our recruitment centres are located in 9 different countries, each recruiting around 400 participants per study (Pilot and RCT) from local schools with differing operating policies. The researchers will make themselves available to participants, staff and parents for the duration of the study supporting retention and troubleshooting problems.

The PO will provide a monthly report, which will be available to all study partners, committees and the EU Commission as required specifying progresses against all deliverables and milestones

8.3. Study Oversight

The governance structure of the BootStRaP Project is displayed in Figure 6. The study will be continuously supervised by two external committees, the Scientific Advisory Board (SAB) and the Ethics Advisory Board (EAB) to ensure all necessary consultation is available for the duration of the BootStRaP project. The sponsor is the University of Hertfordshire, an academic institution, based in the United Kingdom. The University of Hertfordshire leads on management and coordination of the whole project

[figure not shown]

Figure 6: BootStRaP governance structure

including governance, data management, analysis. The Interdisciplinary Centre (IDC) leads on digital data management and analysis. As outlined below, the Project Office is based at the University of Hertfordshire who will provide oversight and coordination for the project (the co-ordinator). The co-ordinator will report directly on a monthly basis to the Steering Committee who will be represented by all the work-package leads (or deputy). The Co-ordinator will also report to the General Assembly and to all the Advisory Boards ensuring seamless coordination and communication between all parties.

8.3.1. Project Office

A Project Office (PO) will be established at UoH, including the co-ordinator, a project manager and support staff. The PO is responsible for central, day-to-day operational management and smooth and timely execution of the project, acting as an accessible helpdesk and consultation and communication point on all matters related to study conduct. In addition, the PO is responsible for assisting the General Assembly (GA), Steering Committee (SC) and the boards of external advisers (Scientific Advisory Board (SAB), Ethics Advisory Board (EAB), Impact Advisory Board (IAB)) on all operational management issues. Data management will be led by the data management committee consisting of the Coordinator, Project Office (UoH), UZL and IDC.

The Project Office (PO) implements standard quality procedures, including meeting procedures, a guide on reporting procedures, standard procedures for data collection and procedures on conflict mediation and corrective actions. The PO will use the CTSN QMS adapting Standard Operating Procedures where necessary.

The Consortium's credentials are enhanced by 3 exceptional Advisory Boards covering all aspects of the project with broad trans-cultural and multidisciplinary expertise, including a Scientific Advisory Board, an Impact Advisory Board, and an Ethics Advisory Board.

